1.2.2 Pharmacology of NC762

The pharmacology of NC762 has been studied in *in vitro* and *in vivo* systems to support its use as an investigational drug in oncology.

In vitro binding studies found that NC762 binds to human B7-H4 with an affinity of 2.99 nM, determined using bio-layer interferometry (BLI). Flow cytometry analysis of NC762 binding to cells stably transduced with B7-H4 exhibited an EC₅₀ of 1.1 nM. Human breast cancer SKBR3 cells that naturally express B7-H4 exhibited an EC₅₀ for NC762 of approximately 1 nM. NC762 also binds to a CD16a-expressing cell line with high avidity. In addition, NC762 binding to SKBR3 cells induced internalization of the antibody. Antibody-dependent cell-mediated cytotoxicity (ADCC) is one of the mechanisms proposed for NC762. NC762 mediated ADCC activity against SKBR3 cells using both a reporter cell line and human PBMCs. No CDC activity was observed.

In vivo, NC762 was effective as a monotherapy in a subcutaneous (SC) human xenograft mouse model. NC762 treatment reduced tumor growth of a human melanoma cell line 624Mel expressing human B7-H4 (624Mel.hB7H4) in the presence of human PBMCs. NK cells but not T cells were involved in restricting tumor growth. Interestingly, NC762 showed activity in the absence of human PBMCs. Immunophenotyping of extracted tumors revealed that NC762 reduced mouse neutrophil in the tumor microenvironment (TME). Furthermore, NC762 with a modified IgG₁ domain that has reduced Fc_YR binding also showed equivalent activity suggesting that NC762 activity also has ADCC-independent mechanisms.

In vitro assays were also conducted to evaluate the risk of cytokine release syndrome (CRS). Using conditions that would have predicted the high risk of CRS for the anti-CD28 mAb TGN1412 (Findlay 2010, Stebbings 2007), NC762 did not promote cytokine release relative to a negative control (anti-RSV) (Synagis®).

For additional information, please refer to the NC762 Investigator's Brochure (IB).

1.2.3 Non-Clinical Safety and Potential Risks of NC762

The toxicology of NC762 has been studied in a variety of *in vitro* and *in vivo* systems to support its use as an investigational drug in oncology.

In the non-GLP, single dose, dose-range-finding (DRF) study, male and female monkeys (N=1/sex/group) were administered with 1, 10, 100 and 300 mg/kg NC762 by 30-min IV infusion. All animals survived up to the end of the study on SD 22. A single dose of NC762 up to 300 mg/kg was very well tolerated in both male and female monkeys. There were no NC762-related observations nor effects on food consumption, body weights, body weight change, hematology, coagulation, clinical chemistry, urinalysis, or peripheral blood leukocyte analysis (PBLA). No NC762-related macroscopic findings were seen at the terminal necropsy. In the single dose DRF study, the highest non-severely toxic dose (HNSTD) was 300 mg/kg/dose of NC762 which resulted in a C_{max} (μg/mL) of 11,400 in males and 10,700 in females; and AUC₀₋₅₀₄ (hr*μg/mL) of 1,010,000 in males and 893,000 in females.

In the GLP-compliant 1-month repeat-dose study, cynomolgus monkeys were administered with 0, 2, 20 or 100 mg/kg NC762 (N=5/sex/group) on SD 1, 15, and 29 by 30-min IV infusion.

Acute toxicity was assessed on SD 31, 2 days after the 3rd dose on three animals/sex/group. Recovery necropsy (2/sex/group) was performed 10 weeks following the last dose on SD 99 to assess for reversibility, persistence, or delayed occurrence of any observed toxicities. There were no mortalities and no NC762-related effects on hematology, clinical chemistry, coagulation, urinalysis parameters, cytokine analysis, gross necropsy findings, organ weights, histopathologic examinations, clinical observations, body weight parameters, blood pressure evaluations, ophthalmology examinations, or electrocardiograph evaluations. The most notable findings were from one male monkey at the highest dose cohort, 100 mg/kg, which showed moderate to marked reduction in neutrophil counts on SD 31 (2 days after the 3rd NC762 dose, as low as 10-20% of its baseline) and on SD 37, 48, 50 and 55. On SD 99 prior to recovery necropsy, its neutrophil counts were back to normal range. Due to the decreased neutrophil counts, this animal was monitored more frequently for signs of illness, but there were no clinical or veterinary findings over the course of the study to suggest an opportunistic infection. B7-H4 was previously reported having effects on mouse neutrophil development ([Zhu 2009](#)). Due to the unique occurrence (1 out of 10 monkeys) in this animal at the highest dose level, with resolution during the non-dosing recovery period, these changes were of uncertain relation to NC762 administration.

Systemic exposure to NC762 appeared to be independent of sex. Following IV infusion administration of NC762, mean C_{max} and $AUC_{0-336hr}$ values for NC762 appeared to increase with increasing dose in an approximately dose proportional manner across the dose range on SD 1 and SD 29. Four NC762 treated monkeys developed anti-drug-antibodies (ADA), which were associated with accelerated clearance. No adverse findings were associated with ADA positivity.

A non GLP-compliant human tissue cross-reactivity (TCR) study was conducted to understand what human tissues will be bound by NC762. Membrane staining with biotinylated-NC762 was limited to hematopoietic precursor cells in the bone marrow and epithelial cells in Fallopian tube, mammary gland (ducts, glands), and placenta (amnion).

Overall, repeat IV administration of NC762 up to 100 mg/kg was well-tolerated and was not associated with any overt toxicity in cynomolgus monkeys. The highest non-severely toxic dose (HNSTD) was 100 mg/kg/dose of NC762, which corresponded with overall mean C_{max} and mean AUC_{0-336} for NC762 on Day 29 of 3,650 μ g/mL and 388,000 hr* μ g/mL, respectively.

1.3 Study Rationale

Immunotherapies have demonstrated an effective anti-tumor immune response and induce significant clinical benefit for a subset of patients with cancer. This study will evaluate immune modulation by targeting B7-H4 expression on tumor cells and its role in creating immune-suppressive tumor microenvironment.

While immunotherapies for cancer have shown great promise, there is still an unmet medical need for additional therapies with novel approaches. Therefore, NC762 may be an effective immunotherapy for some cancer patients.

1.3.1 Rationale for the Safe Starting Dose

The rationale for the proposed Phase 1 starting dose has considered all relevant preclinical pharmacology and toxicology data, including dose-response in human cell-based assays, and anti-tumor effects in mouse tumor models.

NC762 has been well-tolerated and repeated administration of dosages 200-fold higher (on a mg/kg basis) than the planned clinical starting dose were not associated with any adverse toxicities.

A risk assessment for NC762 was performed to support dose selection. Relevant factors for NC762 are discussed below:

The rationale for the proposed Phase 1 starting dose (SSD) of 0.5 mg/kg is based on the collection of preclinical pharmacology and toxicology data, including calculated and experimentally assessed dose-responses in human cell-based assays, and anti-tumor responses in syngeneic tumor models. The FDA Guidance for Industry Estimating the Maximum Safe Starting Dose (SSD) in Initial Clinical Trials for Therapeutics in Adult Healthy Volunteers was used. Since NC762 is a protein administered intravenously with a molecular weight > 100 kDa, mg/kg scaling was used. Relevant *in vivo* pharmacology data from humanized mouse model were used to select the SSD. 1 mg/kg of NC762 displayed some anti-tumor activity in the 624Mel.B7H4 tumor model. Approximately, 9 μ g/mL of NC762 was detected at C_{max} in NSG mouse serum post ip injection with 1 mg/kg NC762, which resulted in a human equivalent dose (HED) of 0.5 mg/kg.

The proposed dosing scheme provides a starting dose that is expected to minimize safety risks and has the potential to provide clinical benefit, which is ethically important in an oncology trial. In the absence of dose-limiting toxicity, the maximum dose that may be explored in the first in human trial will be 20 mg/kg, which is 5 folds lower than the highest non-severely toxic dose (100 mg/kg) determined by the 5-week GLP-compliant repeat-dose tox study in cynomolgus monkeys.

The following summarizes the doses recommended for FIH testing of NC762:

- Highest non-severely toxic dose (HNSTD) in monkeys = 100 mg/kg
- Dose to demonstrate minimum anti-tumor activity in NSG mouse model = 1 mg/kg, delivered ip, ~9 μ g/mL NC762 in mouse serum
- Recommended starting dose = 0.5 mg/kg (5000 mL blood volume and average 80 kg were used for calculation)
- Recommended maximum dose = 20 mg/kg

1.3.2 Rationale for Dosing

Body size-based dosing and fixed dosing of mAbs have been evaluated with the 2 dosing approaches performing similarly, with body size-based dosing not always offering an advantage in reducing variability of exposure. The authors of these studies concluded that either approach may be used in first-in-human (FIH) studies and that fixed dosing is recommended as the preferred approach because of the advantages mentioned above (Wang et al., 2009; Bai et al., 2012).

1.3.3 Rationale for Subject Population for Phase 2

Phase 2 of the study will further evaluate the safety, tolerability, preliminary efficacy, PK, and pharmacologic activity of the RP2D of NC762 in subjects with advanced or metastatic non-small cell lung (squamous cell), hepatocellular carcinoma (HCC), HER2+ breast, and ovarian cancer. The rationale for choosing those tumors is based on the published data as well as our own data showing B7-H4 expression is high in those tumors. A fifth cohort may be included and will enroll patients of a tumor type pending outcomes of the Phase 1.

1.3.4 Rationale for Efficacy Endpoints

Efficacy endpoints of this study are secondary and include objective response rate (ORR), duration of response (DoR), disease control rate (DCR), and progression-free survival (PFS) by investigator assessment based on Response Evaluation Criteria in Solid Tumors (RECIST) v1.1 and modified RECIST (mRECIST).

RECIST v1.1 will be adapted to account for the unique tumor response characteristics seen with immunotherapy ([Chiou & Burotto, 2015](#)). Immunotherapeutic agents may produce antitumor effects by potentiating endogenous cancer-specific immune responses. The response patterns seen with such an approach may extend beyond the typical time course of responses seen with cytotoxic agents and can manifest a clinical response after an initial increase in tumor burden or even the appearance of new lesions. Standard RECIST may not provide an accurate response assessment of immunotherapeutic agents. Therefore, RECIST v1.1 will be used with the following adaptations:

If radiologic imaging shows initial progressive disease, then tumor assessment should be repeated at least 4 weeks but no later than 6 weeks later to confirm disease progression with the option of continuing treatment while awaiting radiologic confirmation of progression.

In subjects who have initial evidence of radiological progression but are clinically stable as defined below, it is at the discretion of the treating physician whether to continue a subject on study drug until repeat imaging is obtained. This clinical judgment decision should be based on the subject's overall clinical condition, including performance status, clinical symptoms, and laboratory data. Subjects may receive treatment while waiting for confirmation of disease progression if they are clinically stable as defined by the following criteria:

- Absence of clinically significant signs and symptoms indicating disease progression
- No decline in Eastern Cooperative Oncology Group (ECOG) performance status
- Absence of rapid progression of disease
- Absence of progressive tumor at critical anatomical sites (e.g., cord compression) requiring urgent alternative medical intervention

If repeat imaging shows < 20% tumor burden compared with nadir, stable or improved previous new lesion (if identified as cause for initial disease progression), and stable/improved nontarget disease (if identified as cause for initial disease progression), then treatment may be continued or resumed. If repeat imaging confirms disease progression due to any of the scenarios listed below, then subjects will be discontinued from study therapy. However, if a subject has confirmed

radiographic progression (i.e., 2 scans at least 4 weeks but no later than 6 weeks apart demonstrating progression) per mRECIST, but the subject is achieving a clinically meaningful benefit, then an exception to continue treatment may be considered after consultation with the medical monitor. Clinically stable subjects at the confirmatory scan should also have no further increase in the target lesions, no unequivocal increase in nontarget lesions, and no additional new lesions develop (non-worsening disease progression) to continue study treatment.

In determining whether the tumor burden has increased or decreased, site study teams should consider all target lesions as well as nontarget lesions (refer to RECIST v1.1 guidelines).

Scenarios where disease progression is confirmed at repeat imaging include the following:

- Tumor burden remains $\geq 20\%$ and at least 5 mm absolute increase compared with nadir
- Nontarget disease resulting in initial disease progression is worse (qualitative)
- New lesion resulting in initial disease progression is worse (qualitative)
- Additional new lesion(s) are found since the last evaluation

When feasible, subjects should not be discontinued until progression is confirmed. This allowance to continue treatment despite initial radiologic progression considers the observation that some subjects can have a transient tumor flare in the first few months after the start of immunotherapy but with subsequent disease response. Subjects who are deemed clinically unstable are not required to have repeat imaging for confirmation of disease progression.

1.4 Summary of Clinical Experience

As this is a FIH study, no data are available in humans. There are no other ongoing studies with NC762.

1.5 Research Hypotheses

NC762 will be adequately tolerated following administration in multiple ascending doses to subjects with refractory solid tumors and that such administration may result in clinical benefit.

2 OBJECTIVES AND ENDPOINTS

2.1 Objectives

2.1.1 Primary Objectives

- 1) To evaluate the safety, tolerability, and dose-limiting toxicities (DLTs) of NC762
- 2) To define an MTD or PAD of NC762

2.1.2 Secondary Objectives

- 1) To evaluate the PK profile of NC762
- 2) To assess preliminary efficacy of NC762
- 3) To evaluate downregulation of B7-H4 expression and changes in tumor infiltrating lymphocytes after NC762 treatment.

2.1.3 Exploratory Objectives

- 1) To assess the immunogenicity of NC762
- 2) To explore biomarkers that may predict the pharmacologic activity of NC762

2.2 Study Endpoints

2.2.1 Primary Endpoints

- 1) Safety and tolerability will be assessed by monitoring frequency, duration, and severity of adverse events (AEs). **Note:** Toxicity grading per NCI CTCAE v5.0.

2.2.2 Secondary Endpoints

- 1) Assessment of PK of NC762 include individual NC762 concentrations in serum and identification of PK parameters.
- 2) Assessment of antitumor activity/efficacy include objective response (OR) and DCR based on RECIST v1.1, DoR, PFS, and overall survival (OS) as per RECIST v1.1 and mRECIST v1.1
- 3) Tumor biopsy analyses to evaluate downregulation of B7-H4 expression and changes in tumor infiltrating lymphocytes after NC762 treatment.

2.2.3 Exploratory Endpoints

- 1) Immunogenicity, defined as the occurrence of ADA to NC762 will be determined.
- 2) Biomarker effects of NC762 in peripheral blood and tumor tissue will be assessed, including but not limited to the following:
 - Whole blood immune cell population profiling/immune-phenotyping.
 - Serum markers of inflammation or immune modulation (cytokine levels).
 - The expression of additional histological biomarkers may also be assessed.

3 STUDY DESIGN

[figure not shown]
3.1 Description of the Study

This is an open-label, nonrandomized, Phase 1/Phase 2 study to determine the safety and tolerability, define the MTD or PAD, and to assess the preliminary efficacy of NC762 in subjects

with advanced or metastatic solid tumors. Subjects will receive NC762 on Day 1 of each cycle. Phase 1 of the study will begin with 14-day cycles; however, alternate dose administration schedules may also be explored depending on PK, PD, biomarker, safety results, and feedback from investigators. The study will be conducted in 2 parts:

- Phase 1 – Dose Escalation (Phase 1a) and Safety Expansion (Phase 1b) will determine the MTD and/or the PAD, defined as a dose that provides a maximal biochemical effect, or an increase in biomarkers of immune activity. It will also define the optimal dose administration schedule and the maximum number of tolerated doses (MNTD).
- Phase 2 – Dose Expansion will evaluate the recommended dose and administration schedule determined in Phase 1 in subjects with advanced or metastatic non-small cell lung (squamous cell), hepatocellular carcinoma, HER2+ breast, and ovarian cancer, or other tumor type as identified with emerging data.

Figure 1: Study Design

RR: Response Rate (ORR) per RECIST v1.1

3.1.1 Phase 1

3.1.1.1 Phase 1a - Dose Escalation

In Phase 1a, subjects with advanced or metastatic solid tumors who progressed after treatment with available therapies that are known to confer clinical benefit, who are intolerant to treatment, or refuse standard treatment will be enrolled. A 3 + 3 design will be utilized to determine the MTD or PAD of NC762.

A minimum of 3 evaluable subjects will be enrolled in each cohort beginning with Cohort 1 (0.5 mg/kg; starting dose). The first 3 evaluable subjects within a cohort will be observed for a DLT observation period of 28 days before the next cohort begins enrollment. Only one subject can be dosed on the first day of dosing for each cohort (additional subjects can begin dosing in ≥ 48 hours). The dose will be escalated if 0 of the first 3 evaluable subjects enrolled has a DLT. If 1 of

the first 3 evaluable subjects enrolled has a DLT, then the cohort will be expanded to include 3 additional evaluable subjects, and if no DLT occurs in the additional 3 subjects, then the dose will be escalated. If a DLT occurs in one-third or more of the expanded cohort, then the MTD will be deemed to be exceeded and the previous dose level will be considered the MTD. Intermediate dose levels below the MTD may be explored pending safety review.

If only 3 subjects were treated at the MTD or PAD, then a minimum of 3 additional evaluable subjects will be enrolled at this dose before it is administered in Phase 2 of the study.

If starting dose exceeds the MTD, the sponsor and investigators will consider dosing NC762 at a lower dose, and/or investigate 0.5 mg/kg at alternate dose schedules, based on available safety, PK, PD, and biomarker data. If an alternate schedule is determined to be safe, re-escalation of NC762 will proceed according to Table 2.

Throughout the treatment period, if > 33% of subjects (a minimum of 6 subjects) experience a \geq Grade 3 toxicity related to study drug after completing \geq 4 cycles, then dose administration will be stopped, and the MNTD will be determined in conjunction with the investigators and sponsor based on all available safety data.

Additional subjects will be enrolled in a cohort to achieve the minimum of 3 evaluable subjects. Subjects who drop out for reasons other than a DLT (e.g., events clearly associated with the underlying disease, disease progression, concomitant medication, or comorbidity) during the 28-day DLT observation period will be considered non-evaluable and will be replaced. Dose modifications should not be made during the DLT observation period without discussion with the medical monitor. Intrasubject dose escalation is not permitted; however, once the RP2D and schedule has been determined, ongoing subjects in Phase 1 may be permitted to escalate to the RP2D only with approval of the medical monitor assuming the subject has not experienced \geq Grade 3 toxicity in previous treatment cycles. The cohorts and dose levels are shown in Table 2.

Table 2: NC762 Dose Levels and Cohorts

Cohort	Dose of NC762
1 (Starting dose)	0.5 mg/kg
2	1.0 mg/kg
3	5.0 mg/kg
4	10 mg/kg
5	20 mg/kg

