A minimum of 3 evaluable subjects will be enrolled in each cohort beginning with Cohort 1 (0.5 mg/kg; starting dose). The first 3 evaluable subjects within a cohort will be observed for a DLT observation period of 28 days, before the next cohort begins enrollment. Only one subject will be dosed on the first day of dosing for each cohort (additional subjects can begin in \geq 48 hours). The dose will be escalated if 0 of the first 3 evaluable subjects enrolled has a DLT. If 1 of the first 3 evaluable subjects enrolled has a DLT, then the cohort will be expanded to include 3 additional evaluable subjects, and if no DLT occurs in the additional 3 subjects, then the dose will be escalated. If a DLT occurs in one-third or more of the expanded

cohort, then the MTD will be deemed to be exceeded and the previous dose level will be considered the MTD. Intermediate dose levels below the MTD may be explored pending safety review. If only 3 subjects were treated at the MTD or PAD, then a minimum of 3 additional evaluable subjects will be enrolled at this dose before it is administered in Phase 2 of the study.

If Cohorts exceed the MTD, the sponsor and investigators will consider dosing NC762 at the lower dose cohorts, and/or investigate 0.5 mg/kg at alternate dose schedules, based on available safety, PK, PD, and biomarker data. If an alternate schedule is determined to be safe, re-escalation of NC762 will proceed according to the table below.

Throughout the treatment period, if > 33% of subjects (a minimum of 6 subjects) experience a \geq Grade 3 toxicity related to study drug after completing \geq 4 cycles, then dose administration will be stopped, and the MNTD will be determined in conjunction with the investigators and sponsor based on all available safety data.

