Subjects who drop out for reasons other than a DLT (e.g., events clearly associated with the underlying disease, disease progression, concomitant medication, withdraw of consent, or comorbidity) during the 28-day DLT observation period will be considered non-evaluable and will be replaced. Dose modifications should not be made during the DLT observation period without discussion with the medical monitor. Intrasubject dose escalation is not permitted; however, once the recommended Phase 2 dose (RP2D) and schedule has been determined, ongoing subjects in Phase 1 may be permitted to escalate to the RP2D with approval of the medical monitor assuming the subject has not experienced \geq Grade 3 toxicity in previous treatment cycles. The cohorts and dose levels are shown in the table below.

Cohort	Dose of NC762
1 (Starting dose)	0.5 mg/kg
2	1.5 mg/kg
3	5.0 mg/kg
4	10 mg/kg
5	20 mg/kg

Phase 1b – Safety Expansion

To evaluate additional PD activity of NC762 and confirm the preliminary safety of the dose escalation cohorts, Phase 1 of the study will include safety expansion cohorts (denoted as Phase 1b) evaluating doses and schedules equivalent to or lower than the highest dose levels determined to be safe and/or doses determined to be pharmacologically active. All doses and schedules explored during the safety expansion will depend on PK, PD, biomarker, and safety results.

Approximately 20 evaluable subjects will be enrolled in the Phase 1b safety expansion, with each dose cohort enrolling up to 10 additional subjects. If < 3 of 10 evaluable subjects

experience a DLT, the cohort will be deemed safe. If > 1 safety expansion cohort is deemed safe, then a recommended dose and schedule will be determined in conjunction with the investigators and sponsor based on all available safety, PK, PD, and biomarker results. The safety expansion cohorts may be conducted in parallel to Phase 2 and may be limited by the sponsor to subjects with specific tumor types to achieve a balance across cohorts.

[figure not shown]
Phase 2 – Dose Expansion

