5 TREATMENT

5.1 Treatment Assignment

5.1.1 Subject Numbering and Treatment Assignment

All subjects will sign an ICF and be assigned a unique subject number with the first 3 digits serving as the site number. The subject numbering process will be managed by the Sponsor/CRO.

Investigative sites must complete all applicable CRFs for subjects consented to the trial, even if the subject is not treated with study drug.

Dose level and cohort assignment will occur at time of subject enrollment and as indicated by the sponsor or designee. Dose level and cohort assignment will be maintained within the CRF per the CRF completion guidelines and managed by the Sponsor/CRO.

All subjects will be assigned to a cohort to receive NC762; there is no placebo.

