
• \geq Grade 2 ocular irAEs• Grade 3 irAEs that do not improve to baseline or at least Grade 1 in < 5 days with appropriate care or with corticosteroid therapy• Grade 4 irAEs regardless of duration.

General

- Inability to receive the planned number of doses within the 28-day DLT period due to toxicity, regardless of grade, will be considered a DLT.
- Combined elevations in serum ALT >3 times the upper limit of normal (ULN) **and** bilirubin >2 ULN in the absence of alkaline phosphatase (ALP) elevation (<2 ULN)
 - Abnormal liver function tests as indicated by the criteria above will be considered a DLT if no other reason can be found to explain the combination of increased liver markers such as viral hepatitis A, B, or C; preexisting or acute liver disease; or another drug capable of causing the observed injury.
- Any death not clearly due to the underlying disease or extraneous causes.

MTD

- In Phase 1 of the study, the MTD will be defined as 1 dose level below that at which \geq one-third of subjects in a cohort have DLTs.
- In Phase 2 of the study, toxicities will continue to be monitored. If the cumulative incidence of DLTs occurs in > 33% of subjects after 6 subjects have been observed for at least 28 days, then further enrollment may be interrupted, and the investigators and sponsor will meet and reassess the MTD. All AEs, regardless of the time of occurrence on study, may be considered in determining the appropriate dose, schedule, and MNTD.

MNTD

- Throughout the treatment period, if > 33% of subjects (minimum of 6 subjects) experience a \geq Grade 3 toxicity related to study drug after completing \geq 4 cycles, then dose administration will be stopped, and the MNTD will be determined in conjunction with the investigators and sponsor based on all available safety data.

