5.4.5 Procedures for Cohort Review and Dose Escalation

Telephone conferences will be scheduled by the sponsor, or sponsor's delegate, with study investigators to review cohort-specific data and overall safety data, to agree on dose escalation, adjudicate individual high-grade AEs as potentially dose-limiting, and guide other major study decisions.

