^aNo more than 2 dose reductions of study drug are permitted (see [Table 2](#)). Subjects should be permanently discontinued from study drug if they have AEs requiring more than 2 dose reductions of study drug.

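### Cohort 2 has two written doses, 1.5 mg/kg in the Protocol Synopsis and 1.0 mg/kg in Table 2, and no readable text says which governs

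*Combined protocol and SAP*

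**What the plan says.** Two tables set out the Phase 1a dose ladder.

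- **Protocol Synopsis, Phase 1a:** "The cohorts and dose levels are shown in the table below". The Cohort 2 row reads 1.5 mg/kg. On moving to an alternate schedule, the synopsis says "re-escalation of NC762 will proceed according to the table below".
- **Section 3.1.1.1:** "The cohorts and dose levels are shown in Table 2". The Cohort 2 row of Table 2 reads 1.0 mg/kg. The matching sentence on alternate schedules says "re-escalation of NC762 will proceed according to Table 2".

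Cohorts 1, 3, 4 and 5 are 0.5, 5.0, 10 and 20 mg/kg in both.

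Other rules depend on the ladder. In Table 3 (section 5.4.2), "the MTD will be defined as 1 dose level below that at which" at least one-third of a cohort has DLTs. Footnote a to Table 4 (section 5.4.6) allows up to two dose reductions and refers to Table 2 for the levels.

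**The concern.** Section 1.4 states that there are no human data, so the dose ladder is a basic safety specification. With two values for Cohort 2, the written plan does not settle the dose of the second cohort or the size of the steps into and out of it.

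Three things follow, two of them conditional:

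- **MTD.** Until Cohort 2 is dosed, the planned level that would become the MTD if Cohort 3 exceeded it has two written values. Once Cohort 2 is dosed, the previous level is whatever was given.
- **Dose reduction.** One reduction from Cohort 3, or two from Cohort 4, lands on the disputed level. If Cohort 2 were run at the synopsis dose and reductions were read from Table 2, the reduced dose would be one that no escalation cohort had tested.
- **Summaries.** Section 9 presents tables by dose group. A Cohort 2 group would mix doses only if both were actually given.

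**Working it through.** **1. The plan's own sample size.** Section 9.2.1 gives at most 5 dose levels under a 3 + 3 design and at most 30 DLT-evaluable subjects. Check: 5 × 6 = 30. The lower end in section 3.3.1 is 15: 5 × 3 = 15. Both figures hold under either table, because both have five levels.

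**2. The two ladders.** Doses are in mg/kg; step = dose of this cohort ÷ dose of the cohort before.

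| Cohort | Synopsis dose | Step | Table 2 dose | Step |
|---|---|---|---|---|
| 1 | 0.5 | – | 0.5 | – |
| 2 | 1.5 | 1.5/0.5 = 3.0 | 1.0 | 1.0/0.5 = 2.0 |
| 3 | 5.0 | 5.0/1.5 = 3.33 | 5.0 | 5.0/1.0 = 5.0 |
| 4 | 10 | 10/5.0 = 2.0 | 10 | 10/5.0 = 2.0 |
| 5 | 20 | 20/10 = 2.0 | 20 | 20/10 = 2.0 |

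The largest step is 3.3-fold in the synopsis and 5.0-fold in Table 2. It is the step into Cohort 3 in both.

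**3. Size of the difference.** (1.5 − 1.0)/1.0 = 50% above the Table 2 value; equivalently, (1.5 − 1.0)/1.5 = 33% below the synopsis value. At the 80 kg average in section 1.3.1: 1.5 × 80 = 120 mg against 1.0 × 80 = 80 mg per infusion.

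**4. Does other text settle it?**

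- Section 1.3.1 fixes only the 0.5 mg/kg start and the 20 mg/kg maximum. Its margins to the 100 mg/kg monkey dose (100/0.5 = 200-fold, 100/20 = 5-fold) do not involve Cohort 2.
- Section 10.2.1 has a precedence clause, but it ranks the protocol against the Clinical Trial Agreement, not the synopsis against the body.
- The re-escalation sentence points to a different table in each place, so it repeats the conflict.
- The Table 4 footnote points to Table 2, but for dose reductions only.

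**5. Extraction or superseded text?** Neither is likely. Both tables are complete and legible row by row, one cell differs while its neighbours agree, and neither table sits in an amendment log.

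**The case against.** The strongest reply is that this is a synopsis cell at odds with the operative table. Table 2 is numbered and listed among the in-text tables, and the body cites it for escalation, re-escalation and dose reduction. The synopsis table is unnumbered and is used only within the synopsis. That is a fair description, but citing a table more often does not make it prevail, and the synopsis cites its own table in the same way.

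The second reply is that controls limit the practical risk. Under section 5.1.1, "Dose level and cohort assignment will occur at time of subject enrollment and as indicated by the sponsor or designee". Cohort 2 cannot open until the first three evaluable Cohort 1 subjects have been observed for 28 days. Section 5.4.5 provides for calls with investigators to "review cohort-specific data and overall safety data, to agree on dose escalation", and section 8.7 says much the same. This stands in part: sites are unlikely to give different doses in parallel. It does not show which Cohort 2 dose the protocol specifies.

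Third, the MTD, dose-reduction and summary effects are conditional. Section 3.1.1.1 also allows intermediate levels below the MTD to be explored, so a dose outside the ladder would not be foreign to the design. This also stands, and the case for correction therefore rests on the contradiction itself. Permission to explore other levels after safety review does not define the planned one.

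Finally, the study schematic and Figure 1 are not shown in the text available here, and the Pharmacy Manual is a separate document. The statement that nothing settles the dose is limited to the readable protocol.

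**Conclusion.** The concern holds with high confidence, and the correction is a must-fix. The protocol gives 1.5 mg/kg in one current table and 1.0 mg/kg in another for the same first-in-human cohort, and no readable rule chooses between them. Those directly affected are the 3 to 6 evaluable subjects of Cohort 2, plus any replaced subjects and any Phase 1b cohort opened at that level. The design, DLT rules and sample size are untouched.

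The milligram comparison assumes the protocol's 80 kg average; the ratios need no assumption. The documents do not say whether Cohort 2 has been dosed.

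**What to change.** Reconcile the Cohort 2 rows of the synopsis table and Table 2 to one dose confirmed by the sponsor. Which dose that should be is not a matter for this review.

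It would also help to name one table as the source for escalation, re-escalation and dose reduction, and to align the references in the synopsis, section 3.1.1.1 and footnote a of Table 4. Once the two cells agree, this is a drafting safeguard against the same divergence recurring.

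If any Cohort 2 subject has already been treated, check the infusion records and summarise by the dose actually received.

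The cost is a short protocol clarification: one table cell, one sentence and a few cross-references, plus the record check if it applies. Sample size and design do not change.
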